2.9. Ethical considerations

The research was conducted in full compliance with the ethical principles of the Helsinki Declaration. Institutional permission and ethical committee approval (Meeting/Decision Number: 10/01; Protocol No: 1070, Date: August 31, 2021) were obtained from the relevant unit of the university where the research was conducted. Prior to data collection, all participants were provided with written information about the purpose, scope, and voluntary nature of the study, and informed consent was obtained. Participants' personal information was kept confidential, and data were used solely for academic purposes. Additionally, the necessary written permissions were obtained from the copyright holders of the measurement tools used in the study.

2.10. Data analysis

Data analysis was performed using IBM SPSS 25.0 (IBM Corp., Armonk, NY, USA). The assumption of normal distribution was evaluated using the Kolmogorov–Smirnov test and supported by skewness and kurtosis values within the ± 2 range. The internal consistency of the scales was determined using Cronbach's alpha coefficient.

Within the scope of statistical analysis, frequency distributions and descriptive statistics were calculated; independent samples t-test and chi-square test were used for intergroup comparisons. Two-Way Mixed ANOVA was applied to examine the effects of group, time, and group × time interaction on education. All necessary assumptions (e.g., normal distribution,

variance homogeneity, sphericity) were tested and found to be met in this analysis. The significance level was set at p<0.005 for all statistical analyses. Additionally, no subgroup analyses were conducted for variables such as age, gender, or academic achievement. All analyses were designed to focus on between-group comparisons.

3. Results

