2.3. Sample, randomization, and prevention of bias

The population of this study consisted of a total of 152 third-year nursing students enrolled in the Child Health and Nursing course. Sample size and power analysis were performed using the G*Power 3.1.9 program. Considering the research design (three measurements and two groups), the following parameters were used for the ANOVA test in repeated measurements: $\alpha = 0.05$, power $(1-\beta) = 0.80$, and moderate effect size (f = 0.25). Accordingly, a minimum of 27 participants per group and a total of at least 54 participants were required. Considering potential data losses, the study was conducted with 44 participants in each group (Cohen, 2013; Faul et al., 2009).

Students were divided into two groups using stratified sampling based on their academic achievement levels. Those with an academic grade point average between 2.00 and 3.00 formed the first stratum, while those with a grade point average between 3.01 and 4.00 formed the second stratum. Within each stratum, participants were assigned to either the intervention or control group in equal numbers using a computer-assisted simple random assignment method with blind allocation. The randomization process was conducted by an independent biostatistician not involved in the study, and no blocking randomization or other restriction methods were used.

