2.6. Application of the flipped learning approach in the intervention group

Students in the intervention group watched lecture videos on relevant topics one week before classroom activities. Students accessed the lecture videos through the https://www.e-pediatri.com platform, developed by researchers using the Tutor LMS system. Tutor LMS was chosen as an effective learning management system due to its user-friendly mobile-supported interface, flexible configuration options, and comprehensive monitoring and evaluation tools. Students logged into the platform with their username and password to access course materials anytime and anywhere and review the materials repeatedly.

Classroom activities were conducted once a week for four weeks, consisting of online sessions lasting approximately 20-25 minutes. These sessions were conducted using interactive techniques in line with the flipped learning approach via the Google Classroom infrastructure integrated into the https://www.e-pediatri.com platform. In the classroom sessions, various student-centered activities such as mini tests, case studies, article reviews, concept maps, and group discussions were implemented to ensure active student participation. These methods were used to help students understand the topics in terms of cause-and-effect relationships and to increase the retention of learning.

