2.7. Application of the self-directed learning approach to the control group

The same educational videos were uploaded simultaneously to the university's Distance Education Center (UZEM) platform for the students in the control group. Students were allowed to watch the videos individually, and no online classroom interaction was conducted throughout the process. The learning process was supported by assignments given to students and online educational materials. The assignments completed by students were evaluated, and feedback was provided to them. The duration of the training was kept equal for both groups.

To minimize contamination risk, the intervention group's training was conducted through the e-pediatri.com platform, while the control group's training was conducted through the university's UZEM platform in sessions of equal duration.

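### The mixed ANOVA treats intervention students taught in shared interactive sessions as independent, so any positive within-session correlation makes the post-training standard errors too small by an amount the documents do not let one fix

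*Combined protocol and SAP*

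**What the plan says.** Section 2.3 describes individual assignment to the two arms within two grade-point strata. The sample size is for a repeated-measures ANOVA, introduced by "Considering the research design (three measurements and two groups" and using a "moderate effect size (f = 0.25"; it gives 27 per group, 54 in total. No design effect is mentioned.

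Delivery then differs by arm. In section 2.6, for the intervention arm: "Classroom activities were conducted once a week for four weeks, consisting of online sessions lasting approximately 20-25 minutes". Activities included case studies, and "concept maps, and group discussions were implemented to ensure active student participation". In section 2.7, controls watched the same videos individually and "no online classroom interaction was conducted throughout the process", though their assignments were marked and returned with feedback.

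The analysis in section 2.10 is: "Two-Way Mixed ANOVA was applied to examine the effects of group, time, and group × time interaction on education". The same section says the necessary assumptions, with normality, variance homogeneity and sphericity given as examples, "sphericity) were tested and found to be met in this analysis". Independence is not among the examples. The limitations in section 7 do not raise it.

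The documents do not state how many session groups there were, how large they were, whether membership was fixed, or how many facilitators led them. No ICC is given.

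**The concern.** Students who share live discussion and an instructor share influences on their later scores. When this happens in one arm only, the design is partially nested: the intervention-arm mean carries a session-level component of variance that an analysis of independent students leaves out. The document itself points to such a mechanism, since section 4.1 attributes retention to active classroom interaction.

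At stake is the stated precision of the primary outcome after training. The month-3 knowledge difference is the more exposed result, because it is about half the post-test difference with a similar standard error, and the conclusion that knowledge was retained rests on it. If all intervention students formed a single class, a second issue arises: the effect of that class and its instructors cannot be separated from the effect of the teaching model.

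**Working it through.** **Inputs.** Means and SDs are from Table 2. Month 3: 92.26 (23.40) versus 77.16 (15.94). Post-test: 105.92 (23.62) versus 78.09 (14.68). I take n = 42 per arm from the abstract and Table 1; Tables 2 and 3 are headed 44. Assumed, because not in the documents: number of session groups k, with size m = 42/k, and the ICC.

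**1. What the ANOVA used.** Error df = df(effect) × F × (1 − η²)/η². For knowledge:
- group: 16.789 × 0.830/0.170 = 82.0
- interaction: 2 × 27.834 × 0.747/0.253 = 164.4

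These match 84 − 2 = 82 and 2 × 82 = 164, so every student counted as an independent unit and 84 students were analysed.

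**2. The planned sample size.** A noncentral F for the interaction with λ = f² × N × 3/(1 − ρ) and ρ = 0 gives λ = 0.0625 × 54 × 3 = 10.125 and power 0.809 at N = 54. The stated 54 therefore reproduces without any allowance for clustering. Section 2.3 does not state ρ or which F test was used, so this match is one possible route.

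**3. Month-3 knowledge under independence.** The document reports no between-arm month-3 test, so I rebuilt one.
- Difference: 92.26 − 77.16 = 15.10
- Variances of the means: 23.40²/42 = 13.04 and 15.94²/42 = 6.05
- SE = √(13.04 + 6.05) = 4.37; t = 3.46; Welch df 72.3; p = 0.0009; 95% CI 6.4 to 23.8

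With 44 per arm, p = 0.0007.

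**4. One-arm clustering.** SE = √(DE × 13.04 + 6.05), with DE = 1 + (m − 1) × ICC. At ICC 0.05:

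| Session groups | m | DE | SE | 95% CI, normal reference |
|---|---|---|---|---|
| 1 | 42 | 3.05 | 6.77 | 1.8 to 28.4 |
| 2 | 21 | 2.00 | 5.67 | 4.0 to 26.2 |
| 4 | 10.5 | 1.475 | 5.03 | 5.2 to 25.0 |

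The normal-reference interval reaches zero when DE = [(15.10/1.96)² − 6.05]/13.04 = (59.35 − 6.05)/13.04 = 4.09. That is ICC 3.09/41 = 0.075 for one group, 3.09/20 = 0.154 for two and 3.09/9.5 = 0.325 for four. The one-group figure is a benchmark only: a single class leaves no degrees of freedom for between-class variance, so no valid p-value exists.

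**5. Few-cluster degrees of freedom.** With V₁ = DE × 13.04 and V₂ = 6.05, Satterthwaite df = (V₁ + V₂)²/[V₁²/(k − 1) + V₂²/41]. At ICC 0.05:
- two groups: V₁ = 26.07, df 1.52, t = 2.66, p = 0.155
- three groups: p = 0.058
- four groups: V₁ = 19.23, df 5.15, t = 3.00, p = 0.029

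At ICC 0 with two groups, p is already about 0.07. Much of the loss with two groups therefore comes from the small df and not from the larger SE.

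**6. Post-test knowledge.** Difference 27.83, independent SE 4.29, t = 6.49. With a normal reference, one group of 42 needs ICC 0.336 to reach p = 0.05. With few-cluster df and two groups, SE is 5.63 and p about 0.07 at ICC 0.05, and p about 0.11 at ICC 0.10. With four groups at ICC 0.05, p is about 0.003.

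**The case against.** The strongest reply is that the result depends on two unknowns. Section 2.6 does not say that all 42 met together, and nothing in the documents supports a particular ICC. If the ICC is zero, the reported standard errors are right. If groups were small, little changes: with six groups of 7 and a normal reference, month-3 p stays below 0.05 until ICC 0.515. This stands. A reader might infer that the intervals are shown to be too narrow by a known amount, or that month-3 significance is lost; neither follows.

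Second, students were randomised individually, so comparing the two packages as delivered, with this class and these instructors, is a legitimate target. This also stands. With one class, the issue is how far the conclusion reaches, and no reanalysis can settle it.

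Third, a reader might extend the problem to every between-arm comparison. The pre-test was taken before any session, so session clustering cannot affect it. Nor is it certain that the control arm has no correlation, since its assignments received feedback.

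Fourth, the month-3 test above is unadjusted and is not one the document reports; the published interaction F was not re-tested for clustering. The list of assumptions in section 2.10 is also illustrative, so leaving out independence does not prove that it was ignored. Both are fair. But the ANOVA has no session term, its error df are those of 84 independent students, and the statement that assumptions were met is not qualified.

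**Conclusion.** The concern holds as a question of precision and of reporting. For any positive within-session correlation, the standard errors of the post-training between-arm comparisons are too small. How much too small cannot be determined from the documents. At an assumed ICC of 0.05, the month-3 knowledge SE rises from 4.37 to between about 5.0 (four groups) and 6.8 (one group).

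Whether the month-3 difference stays below 0.05 depends on group number, ICC and reference distribution. With large-sample df it does so up to ICC about 0.075 (one group, benchmark only) or 0.15 (two groups). With few-cluster df at ICC 0.05 it does so for four groups (p about 0.03) but not for two (p about 0.155).

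Two stronger readings are not supported. One is that the post-test difference is safe whatever the clustering: with two groups and few-cluster df it is not. The other is that month 3 fails the trial's own threshold at a very small ICC. That relies on "The significance level was set at p<0.005 for all statistical analyses" in section 2.10, while section 2.3 uses 0.05. The two must be reconciled separately before either serves as a benchmark.

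**What to change.** In section 2.10:

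- Report the number and size of the intervention session groups, whether membership was fixed, and who facilitated each. The remaining steps depend on this.
- Keep the ANOVA and add a table of SE and 95% CI for the post-test and month-3 between-arm differences over ICC 0.01 to 0.10. Give no p-values for the one-class case.
- If there were more than two or three session groups, so that the variance can be estimated, add a partially nested mixed model: a random session-group effect in the intervention arm only, controls as single units, and small-sample df.
- If there was one group, state that the class and instructor effect cannot be separated from the teaching model and that the conclusion is conditional on this class.
- In every case, reword the assumptions statement so that it excepts independence.

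The cost is one table and possibly one further model from data already held. The downside is wider intervals and a less certain month-3 retention conclusion. With very few session groups the nested model could be close to uninformative, which is why the table comes first.

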The study's sampling process, group distribution, randomization, follow-up, and number of samples analyzed are presented in Figure 1 in accordance with the CONSORT 2010 guidelines. Statistical analysis and reporting were performed by an independent statistician. Since the intervention was directly integrated into the students' educational process in this study, blinding could not be applied from the perspective of the participants (students) and the researchers who administered the intervention. However, to minimize bias, blinding was ensured during the data analysis process. In this context, a data set that did not contain information about which intervention the groups received, but was only coded (e.g., Group A, Group B) and anonymized, was presented to the independent statistician; the statistician conducted the analyses without knowing the identity of the groups. Thus, objectivity was maintained and the risk of systematic bias was reduced during the analysis and reporting stages. Additionally, a chi-square test based on academic achievement scores was conducted to assess the homogeneity of the groups at the baseline level, and it was determined that the groups were at a similar level (Table 1).

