2.8. Data collection

In the study, pre-tests were administered before the training; post-tests were administered one month after the completion of the training modules, and retention tests were administered three months after the completion of the training.

All data collection for the intervention and control groups was conducted online. The questionnaires and scales used were distributed to participants via Google Forms, and students were asked to fill out the forms on their own devices. No changes were made to the primary (pediatric pain management knowledge level) and secondary (learning motivation) outcome measures defined at the beginning of the study during the data collection process.

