The use of this approach in practice-based courses such as pediatric nursing can positively influence not only students' knowledge levels but also their motivation and attitudes toward learning. In this regard, giving more space to innovative learning approaches such as the flipped classroom model in nursing curricula will contribute to the development of students' academic achievements as well as their clinical competence after graduation.

Future research focusing on evaluating the long-term effects of the flipped classroom model in different nursing courses and examining its outcomes on students with different learning profiles will contribute to strengthening evidence-based data on the model's effectiveness.

7. Limitations and strengths

One of the prominent strengths of this study is its randomized controlled experimental design, which was structured to test the research hypotheses. The statistical similarity of the intervention and control groups in terms of their initial descriptive characteristics increased the internal validity of the group comparisons. The validity and reliability of the measurement tools used have been previously reported, supporting the quality of the data obtained. The intervention protocol was structured, developed based on expert opinions, and implemented with equal content and duration for both groups. The use of two different digital platforms (epediatri.com and UZEM) to minimize contamination risk was supported by careful planning of synchronization and access timing. Additionally, the statistical analyses were conducted by an independent expert, and the study results were reported in accordance with the CONSORT 2010 () checklist, which are among the factors enhancing the methodological strength of the study.

On the other hand, the study has some limitations. The fact that the research was conducted at a single center and included only nursing students from one university limits the generalizability

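### Section 2.10 uses the pre-test only as one level of the outcome, never as a covariate, so the between-group comparisons are less precise than the data allow

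*Combined protocol and SAP*

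**What the plan says.** The two research hypotheses at the end of section 1 are between-group: knowledge and motivation scores are expected to be higher with the flipped classroom than in control. Section 2.10 also says that the analyses focus on between-group comparisons.

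Section 2.8 records that "pre-tests were administered before the training", with a post-test and a month-3 retention test afterwards. In section 2.10 the model is described in one sentence: "Two-Way Mixed ANOVA was applied to examine the effects of group, time, and group × time interaction on education". Apart from that, only t-tests and chi-square tests are named for comparing groups. No ANCOVA, baseline covariate or change-score model is described. Tables 2 and 3 show the pre-test as a row under the same group, time and interaction statistics as the two follow-ups.

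Baseline comparability is argued by testing. Section 2.3 reports that "a chi-square test based on academic achievement scores was conducted to assess the homogeneity of the groups at the baseline level", and section 7 says that "The statistical similarity of the intervention and control groups in terms of their initial descriptive characteristics increased the internal validity of the group comparisons".

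The sample size in section 2.3 assumes two groups, three measurements, alpha 0.05, power 0.80 and a "moderate effect size (f = 0.25"), giving 54 in total. It does not say which ANOVA effect f describes or what correlation was assumed. Section 2.10 gives a different threshold: "The significance level was set at p<0.005 for all statistical analyses".

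**The concern.** A pre-test on the same scale is usually the best available predictor of the follow-up score, and it is free because it has already been collected. Used as an outcome level, it helps less than it could, for two reasons.

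- **Group main effect.** This averages the group difference over all three visits. One is the pre-test, where randomisation makes the expected difference zero. The result is diluted and is not the treatment effect at any visit.
- **Group × time interaction.** This compares changes between visits. Subtracting the pre-test is the same as fixing the baseline slope at 1. If the true slope is nearer 0.5, part of the pre-test noise is added back and a chance imbalance is over-corrected.

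At stake are the size and precision of the estimates. The document draws conclusions about the amount and retention of benefit, and the control group started 3.15 points higher on motivation.

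**Working it through.** **Inputs.** Means, SDs and F values come from Tables 2 and 3. I take n = 42 per arm, as in the abstract. The table headers say 44, but the printed partial eta squared fits error df 82: 16.789/(16.789 + 82) = 0.170.

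**1. The plan's own sample size.** For a within-between interaction, λ = N·m·f²/(1 − r), with df 2 and 2(N − 2). With m = 3, f = 0.25 and r = 0, N = 54 gives power 0.809. This reproduces 54.

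**2. The pre-test was an outcome level.** The knowledge differences (intervention minus control) are −1.29, 27.83 and 15.10, mean 13.88.
- Group SS = 3 × 42 × 2 × (13.88/2)² = 12,137. Dividing by F = 16.789 gives MS between = 722.9.
- Interaction SS = 21 × (15.17² + 13.95² + 1.22²) = 8,951. Dividing by 2 and by F = 27.834 gives MS within = 160.8.
- The time F, treated the same way, gives 160.7. The two agree only if all three visits are levels of the outcome.

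**3. Implied correlation (compound symmetry).** r = (MSB − MSW)/(MSB + 2·MSW).
- Knowledge: 562.1/1,044.5 = 0.54.
- Motivation (MS 394.4 and 104.6): 289.8/603.6 = 0.48.
- Mixing printed SDs with the F values widens this. Motivation has mean variance 174 from the SDs, so 1 − 104.6/174 = 0.40 and (394.4/174 − 1)/2 = 0.63. Knowledge gives 0.44 to 0.58.

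**4. Single-visit precision.** In units of 2σ²/n, the variances are raw 1, change 2(1 − r), ANCOVA 1 − r². At r = 0.5 these are 1, 1 and 0.75, so ANCOVA is 25% below both. At r = 0.40 the cut is 16% against raw and 30% against change. At r = 0.63 it is 40% and 18%.

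Month-3 knowledge with the printed SDs and r = 0.5 in each arm:
- Raw: √[(23.40² + 15.94²)/42] = 4.37, half-width 8.7.
- Change: √[(460.9 + 316.5)/42] = 4.30, half-width 8.6.
- ANCOVA: common slope (219.8 + 152.9)/(353.1 + 368.3) = 0.517 and residual variances 414.6 and 194.4, so √(609.0/42) = 3.81, half-width 7.6.

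**5. Estimates.**
- Knowledge, mean of the two follow-ups: 21.47 + 0.54 × 1.29 ≈ 22.2 (SE about 2.8), against 13.88 (SE 3.39) for the group main effect.
- Month-3 motivation: raw 101.50 − 85.61 = 15.89; change 15.89 + 3.15 = 19.04; adjusted with slope 0.5, 15.89 + 1.58 ≈ 17.5 (17.2 to 17.9 for slopes 0.40 to 0.63).

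**6. Information, with equal effects at both follow-ups.** Effective variances at r = 0.5:
- Three-level group effect: [(1 + 2r)/3]/(2/3)² = 1.5.
- Mean follow-up, no covariate: (1 + r)/2 = 0.75.
- ANCOVA: (1 + r)/2 − r² = 0.5.

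The ratio of ANCOVA to group effect is 3.0. A factor of 2 comes from leaving the pre-test out of the average and 1.5 from the covariate. Against the interaction the ratio is 3/(1 + 2r) = 1.5, and the interaction also spends a second degree of freedom.

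**7. Power** at n = 42 per arm, r = 0.5, alpha 0.05, for three readings of f = 0.25. Noncentralities, with d the follow-up difference in SDs: group (2/3)nd²/(1 + 2r); interaction nd²/[3(1 − r)]; ANCOVA nd²/[(1 − r)(1 + 2r)].

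| Reading of f | d | Group | Interaction | ANCOVA |
|---|---|---|---|---|
| Two groups at each follow-up (2f) | 0.50 | 0.46 | 0.65 | 0.89 |
| Group effect averaged over three visits (2f × 3/2) | 0.75 | 0.79 | 0.95 | 0.998 |
| Interaction (f√18), which reproduces N = 54 | 1.06 | 0.975 | 0.999 | about 1 |

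A 6,000-trial simulation of the first row gave 0.46, 0.65 and 0.89. At alpha 0.005 that row becomes 0.16, 0.32 and 0.64.

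**The case against.** The strongest reply is that nothing invalid was done. The abstract and section 3.2 rest chiefly on the interaction, which uses each student's own pre-test and holds its error rate. All reported p-values are below 0.001, under both 0.05 and 0.005. For month-3 knowledge the gain is about one point of half-width around a 15.1-point difference. All of this stands, and it limits the point to efficiency and estimation.

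Four further limits also stand.
- The threefold ratio concerns the group main effect, and most of it comes from dropping the pre-test from the average. A reader might credit all of it to the covariate; step 6 shows otherwise.
- The 1.5 ratio against the interaction assumes equal effects at both follow-ups. With knowledge effects of 0, 27.83 and 15.10, the interaction gets (14.31² + 13.52² + 0.79²)/(1 − 0.5) = 776 and ANCOVA 21.465²/0.5 = 921, a ratio of about 1.2. The single-visit gain in step 4 does not depend on this.
- The motivation inputs are weak. The printed post-test mean of 120.66 exceeds the scale maximum of 120 given in section 2.2.3, and the variance is 201 from the mean squares against 174 from the SDs.
- An analysis chosen after the results are known cannot simply be called confirmatory.

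None of these removes the precision gain or the spread of about 3 points in month-3 motivation.

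**Conclusion.** The point holds as a loss of efficiency. The pre-test is used only as an outcome level, although the hypotheses are between-group and a covariate was available at no cost. At a correlation of about 0.5 (range 0.40 to 0.63, derived under compound symmetry and not stated in the document), adjustment removes about a quarter of single-visit variance. Knowledge at follow-up is then summarised by about 22 points instead of a diluted 13.88. Month-3 motivation moves between 15.9 and 19.0 depending on method; the adjusted 17.5 is approximate.

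Two stronger readings are tempting and are not supported. One is that the plan gives up much of its power. That follows only if f = 0.25 means 0.5 SD at follow-up; under the reading that reproduces the stated 54, the ANOVA tests already have power of 0.975 or more. The other is that the findings are biased or would reverse. The interaction test is valid, and the reported effects are large enough that significance is not expected to change.

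The baseline tests are a side issue. Equal assignment within each GPA stratum forced the 21/21 split, so its p-value of 1.00 says nothing about comparability.

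**What to change.** In section 2.10, add an estimate of the group difference for knowledge (H1) and for motivation (H2). Use either an ANCOVA or a repeated-measures model with only the post-test and month 3 as outcomes. Include the same scale's pre-test and the GPA stratum as covariates; the stratum belongs there because assignment was stratified on it. Report the adjusted differences with 95% confidence intervals alongside the original mixed ANOVA, and label them a post hoc re-analysis because the data are already known. In sections 2.3 and 7, stop citing non-significant baseline tests, including the forced GPA split, as evidence that the groups were comparable.

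The cost is one re-run in SPSS on data already held, one degree of freedom per covariate, and slightly different published estimates. No new data are needed.
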